1.0 STUDY ADMINISTRATIVE INFORMATION AND CLINICAL STUDY PRINCIPLES

1.1 Clinical study principles

This study will be conducted with the highest respect for the individual participants in accordance with the requirements of this clinical study protocol and also in accordance with the following:

- The ethical principles that have their origin in the Declaration of Helsinki.
- Ethical Guideline for Clinical Research (the Ministry of Education, Culture, Sports, Science and Technology and the Ministry of Health, Labour and Welfare, December 22, 2014).
- Good Clinical Practice: Consolidated Guideline (ICH: International Conference on Harmonization of Technical Requirement for Registration on Pharmaceuticals for Human Use. E6)
- All applicable laws and regulations, including, without limitation, data privacy laws and conflict of interest guidelines.

1.2 Clinical study implementation system

This study will be conducted in accordance with the requirements of this clinical study protocol designed and prepared by the sponsor and also in accordance with the following. Other study administrative structures are shown in the separate documents.

Sponsor

Japan Medical Affairs, Japan Pharma Business Unit, Takeda Pharmaceutical Company Limited

The sponsor shall be responsible for matters related to planning/preparation, implementation/operation, and results/reporting in this clinical study. Methods of supervision of the contractor entrusted with the services related to this clinical study will be described in the procedure to be prepared separately.

Expenses* required for the operation of this clinical study will be paid by the sponsor.

* : Based on the “Consignment Service Contract,” expenses incurred for the services of Office of Clinical Study, monitoring, registration/allocation center, and statistical processing shall be paid to the contractor entrusted with services related to this clinical study. Expenses agreed by the study site shall be paid to the site based on the “Research Expense Standard.”

Chair of the Clinical Study Steering Committee:

PPD

Terms in this protocol are defined as follows:

Study site:

A corporation, governmental agency and sole proprietor conducting the study, excluding cases where only a part of the services related to storage of samples/information, statistical processing and other studies are entrusted.

Investigators:

Principal investigators and other parties involved in conduction of the study (including operations at institutions involved in collection/distribution of samples/information). Those involved only in providing existing samples/information outside the study sites and those engaged in part of the entrusted operations related to the study are excluded.

Principal Investigator:

An investigator who is engaged in implementation of the study and integrates the operations involved in this study at an affiliated study site.

Chief executive of the study site:

A representative of a corporation, head of a governmental agency, or a sole proprietor

Study subject:

A subject (including a dead subject) who meets any of the following:

1. Subjects being studied (including those who have been asked to be studied)
2. Subjects from whom existing samples/information to be used in the study have been obtained.

CONFIDENTIAL

Table of Contents

2.0 STUDY SUMMARY

Sponsor: Takeda Pharmaceutical Company Limited	Study drug: Trelagliptin
Study title: Study of the QOL evaluation of Trelagliptin in patients with type 2 diabetes mellitus	
Protocol number: Trelagliptin-4002	
Clinical study design: This is a multi-center, randomized, open-label, parallel-group comparison study to assess the reduction in treatment burden during the administration of a DPP-4 inhibitor (trelagliptin or a daily DPP-4 inhibitor) for 12 weeks in patients with type 2 diabetes on diet and exercise therapy only. Subjects who are determined to be eligible based on the results of eligibility assessment after informed consent has been obtained will be randomized to either the study drug (trelagliptin) group or the comparative drug (daily DPP-4 inhibitor) group. Randomization was stratified by the total score (<80% (score 139.4), ≥80% (score 139.4*)) for total score of the “Diabetes Therapy-Related QOL (DTR-QOL) Questionnaire” and “HbA1c (<8.0%, ≥8.0%)” at the start of the screening period. * A scale of 1 to 7 with 7 as the best was used for each QOL question item, and total score calculated by adding up scores of each question was expressed as a percentage of the maximum total score (i.e., the best score [203] = 100%; the worst score [29] = 0%).	
Objectives: The objective is to assess the reduction in treatment burden during 12 weeks of trelagliptin administration in patients with type 2 diabetes on diet and exercise therapy only	
Subjects: Patients with type 2 diabetes on diet and exercise therapy alone	
Planned number of study subjects: As the number of randomized subjects: The study drug (Trelagliptin) group 120 subjects The comparative drug (daily DPP-4 inhibitor) group 120 subjects	Number of study sites: Approximately 15
Dose and method of administration: The study drug (Trelagliptin) group: Trelagliptin 100 mg is orally administered once weekly. Trelagliptin	Route of administration: Oral

CONFIDENTIAL

50 mg is orally administered once weekly in patients with moderate renal impairment. The comparative drug (Daily DPP-4 inhibitor) group: An inhibitor is orally administered at the dosage and administration in the package inserts for each drug.	
Duration of treatment: 12 weeks	Duration of evaluation: 16 weeks (Screening period: 4 weeks; treatment period: 12 weeks)
Inclusion criteria: Eligibility of study subjects shall be determined in accordance with the following criteria. 
1. Patients diagnosed as type 2 diabetes.2. Patients with a stable diet and exercise therapy only for at least 12 weeks prior to the start of the screening period.3. Patients who require a DPP-4 inhibitor treatment.4. Patients with HbA1c $\geq 6.5\%$ and $< 10.0\%$ at the start of the screening period.5. Patients who completed DTR-QOL questionnaire at the start of the screening period.6. Patients who have received less than 2 types of medication for treatment of comorbidities (such as hypertension or dyslipidemia) at the start of the screening period (any number of daily doses).7. Patients who, in the opinion of the principal investigator or the investigator, are capable of understanding the content of the clinical study and complying with the study protocol requirements.8. Patients who can provide the written informed consent prior to the initiation of any study procedures.9. Patients aged ≥ 20 years at the time of informed consent.10. Outpatient.	
Exclusion criteria: Study subjects meeting any of the criteria below shall not be included in this study. 
1. Patients who are receiving any oral anti-diabetic medication for the treatment of type 2 diabetes at the start of the screening period.2. Patients diagnosed as type 1 diabetes.	

3. Patients with severe renal impairment or renal failure (e.g., eGFR <30 mL/min/1.73 m² or on dialysis).
4. Patients with serious heart disease or cerebrovascular disorder, or serious pancreatic, blood, or other disease.
5. Patients with a history of gastrointestinal resection.
6. Patient with a proliferative diabetic retinopathy.
7. Patient with malignancy.
8. Patients with a history of hypersensitivity or allergy to DPP-4 inhibitors.
9. Pregnant, lactating or postmenopausal women.
10. Patients who may need to add or discontinue concomitant medication or change the dose during the study period.
11. Patients who will require treatment with a prohibited concomitant medication during the study period.
12. Patients participating in other clinical studies.
13. Patients assessed ineligible in the study by the principal investigator or the investigator.

ENDPOINTS:

<Primary endpoint>

Change from baseline (Week 0) in total score for all question items in the DTR-QOL Questionnaire at the end of the treatment period (Week 12).

<Secondary endpoints>

Efficacy assessment:

- Changes in the total score for each factor provided through the DTR-QOL Questionnaire [Factor 1: Burden on social activities and daily activities (13 questions in all), Factor 2: Anxiety and dissatisfaction with treatment (8 questions in all), Factor 3: Hypoglycemia (4 questions in all) and Factor 4: Treatment satisfaction (4 questions in all)] at each assessment time point.
- Change in the total score for all questions in the DTR-QOL Questionnaire at each assessment time point.
- Change in the total score for treatment satisfaction in the Diabetes Treatment Satisfaction Questionnaire (DTSQ) at each assessment time point.
- Changes in the total scores for all questions in the DTR-QOL Questionnaire and the total score

CONFIDENTIAL

for treatment satisfaction in the DTSQ, stratified by the following factors at the start of the treatment period (Week 0) within each treatment group.

- Use of medication for treatment of comorbidities
- Number of daily doses of medication for treatment of comorbidities (<2 times or \geq 2 times)
- Total number of daily tablets of medication for treatment of comorbidities (<2 tablets or \geq 2 tablets)
- Number of doses of the study drug or comparative drug (once weekly, once daily or twice daily)
- Changes in the scores per question in the DTR-QOL Questionnaire at each assessment time point.
- Changes in the scores per question in the DTSQ at each assessment time point.

Safety assessment:

- Adverse events
- Incidence of hypoglycemia
- Hospitalization for type 2 diabetes (duration and number, excluding educational hospitalization without worsening of diabetes)

<Other Endpoints>

- Laboratory tests [HbA1c, fasting blood glucose, fasting insulin, fasting glucagon, glycoalbumin, 1,5-AG, serum creatinine, urinary 8-OHdG (using a correction value of uric creatinine (8-OHdG/creatinine)) and urinary creatinine]
- Treatment compliance
- The Basic Information on Study Subject (Your Basic Profile)

STATISTICAL ANALYSIS METHODS:

<Analysis Sets>

Two analysis sets comprising the “Full Analysis Set (FAS)” and the “Safety Population” will be established. The FAS used as the main efficacy analysis set is defined as “randomized subjects who receive at least one dose of trelagliptin or daily DPP-4 inhibitor.” The safety population is defined as “subjects who receive at least 1 dose of trelagliptin or daily DPP-4 inhibitor.”

<Primary endpoint>

- Change from baseline (Week 0) in total score for all question items in the DTR-QOL Questionnaire at the end of the treatment period (Week 12).
 - (1) A comparison between the treatment groups will be carried out based on the ANCOVA model using a change in the total score by the end of treatment [the end of the treatment period (Week 12) - baseline (Week 0)] as a dependent variable; the total score at the baseline (Week 0), the total score of the DTR-QOL Questionnaire (<80% or ≥80%) at the start of the screening period and HbA1c (<8.0% or ≥8.0%) at the start of the screening period as covariates; and a treatment group as an independent variable. The level of significance will be 5% (two-sided).

<Secondary endpoints>

Efficacy endpoints:

- Change in the total score for each factor provided through the DTR-QOL Questionnaire [“Factor 1: Burden on social activities and daily activities (13 questions in all)”, “Factor 2: Anxiety and dissatisfaction with treatment (8 questions in all)”, “Factor 3: Hypoglycemia (4 questions in all)”, and “Factor 4: Treatment satisfaction (4 questions in all)”] at each assessment time point.
- Change in the total score for all questions in the DTR-QOL Questionnaire at each assessment time point.
- Change in the total score for treatment satisfaction in the DTSQ at each assessment time point.
 - (1) Summary statistics [sample size, mean, standard deviation (SD), maximum, minimum and quantile] and the two-sided 95% confidence interval (CI) for means per treatment group at each assessment time point will be calculated to plot the changes in means and SDs. Point estimates and the two-sided 95% CI for differences between the treatment groups will also be calculated.
 - (2) Changes from the baseline (Week 0) to each assessment time point will be calculated to be similarly analyzed to 1) above.
 - (3) The analyses below carried out on the total score for each factor provided through the DTR-QOL Questionnaire, and on the total score for treatment satisfaction in the DTSQ: A comparison between the treatment groups will be carried out based on the ANCOVA model using a change in the total score by the end of treatment [the end of the treatment period (Week 12) - baseline (Week 0)] as a dependent variable; the total score at the baseline (Week 0), the total score of “the DTR-QOL Questionnaire (<80% or ≥80%)” at the baseline (Week 0) and “HbA1c (<8.0% or ≥8.0%)” at the baseline (Week 0) as covariates; and a treatment group as an independent variable. The level of significance will

be 5% (two-sided). Note that the total score for all questions in the DTR-QOL is out of the scope of the analysis.

- (4) To indicate the changes in the total scores for all questions in the DTR-QOL Questionnaire and the total score for treatment satisfaction in the DTSQ, the summary statistics and two-sided 95% CI for means per treatment group will be calculated, with stratification by the following factors at the start of the treatment period (Week 0):
 - Use of medication for treatment of comorbidities
 - Number of daily doses of medication for treatment of comorbidities (<2 times or \geq 2 times)
 - Total number of daily tablets of medication for treatment of comorbidities (<2 tablets or \geq 2 tablets)
 - Number of doses of the study drug or comparative drug (once weekly, once daily or twice daily)
- Changes in the scores per question in the DTR-QOL Questionnaire at each assessment time point.
- Changes in the scores for per question in the DTSQ at each assessment time point.
 - (1) Summary statistics for measurements and the changes from the baseline (Week 0) will be calculated per treatment group.

Safety endpoints:

Frequency tables will be prepared for the incidences of adverse events, hypoglycemia, and hospitalization (duration and number) for type 2 diabetes after the first administration of the study drug or comparative drug in the “safety population” in each treatment group.

<Other Endpoints>

Summarizations below will be performed in the "full analysis set" (FAS).

- Laboratory tests
Summary statistics for measurements and the changes from the baseline (Week 0) will be calculated per treatment group to plot the changes in means and SDs.
- Treatment compliance
Treatment compliance of each study subject will be calculated and summary statistics of compliance per treatment group will be presented.
- The Basic Information on Study Subject (Your Basic Profile)
Frequency of answers to each question at each visit will be analyzed per treatment group.

CONFIDENTIAL

Rationale for the number of planned study subjects:

In this clinical study, to discuss the changes in the total score for all questions in the DTR-QOL Questionnaire from the baseline (Week 0) to the end of the treatment period, as the primary endpoint, mean changes in the daily DPP-4 inhibitor and trelagliptin groups were assumed as 14.4% and 19.0%, respectively. The mean change in the daily DPP-4 inhibitor group was assumed by reference to the data on a sodium glucose transporter 2 (SGLT2) inhibitor, from the previous research; and that in trelagliptin group was assumed by reference to the data from the validation trial of the DTR-QOL Questionnaire. The common SD was assumed as 12.1 % considering the former assumption. When 5% of significance level (two-sided) is based for the analysis of the primary endpoint, 110 subjects per group would be needed to ensure 80% power in comparisons between the trelagliptin group and daily DPP-4 inhibitor group. As this is a study on treatment for type 2 diabetes with DPP-4 inhibitors currently used in the medical setting, the number of randomized subjects was established as 120 subjects per group, for a total of 240 subjects, assuming a type 2 diabetes treatment discontinuation rate of 8%*.

*Based on the results for Topic 2 of the “Strategic Studies on the Prevention of Diabetes” (JDOIT-2), the annual discontinuation rate for the “usual care group” without intervention is approximately 8%.

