9.1.9 DTR-QOL Questionnaire

Subjects will answer the DTR-QOL Questionnaire (all 29 questions)⁵⁾ regarding the diabetes therapy being conducted at each assessment time point during the screening period and treatment period. The investigator will instruct the subjects to answer all questions truthfully and record the answer of each question of the DTR-QOL Questionnaire (29 questions in total) on the CRF.

[Calculation of the total score based on answers of the DTR-QOL Questionnaire]

- Calculation method of the total score of Factor 1: "burden on social activities and daily activities" (13 questions in all)

Every score of the question number 1-13 will be simply added up, and the total figure will be subsequently converted to percentage [the best (91) and worst (13) scores will be equivalent to 100% and 0%, respectively].

- Calculation method of the total score of Factor 2: "anxiety and dissatisfaction with treatment" (8 questions in all)

Every score of the question number 14 and 19-25 will be simply added up, and the total figure will be subsequently converted to percentage [the best (56) and worst (8) scores will be equivalent to 100% and 0%, respectively].

- Calculation method of the total score of Factor 3: "hypoglycemia" (4 questions in all)

Every score of the question number 15-18 will be simply added up, and the total figure will be subsequently converted to percentage [the best (28) and worst (4) scores will be equivalent to 100% and 0%, respectively].

- Calculation method of the total score of Factor 4: "treatment satisfaction" (4 questions in all)

Each score of the question number 26-29 will be converted into reverse (i.e., 1 will be converted to 7, 7 will be converted to 1, and so on. The converted scores, where 7 is the best and 1 is the worst, have the opposite sequence of the original scores). Then, the converted scores will be simply added up, and the total figure will be subsequently converted to percentage [the best (28) and worst (4) scores will be equivalent to 100% and 0%, respectively].

- Calculation method of the total score of all questions

Each score of the question number 26-29 will be converted into reverse, as described above, and then these converted scores and original scores of the question number 1-25 will be simply added up. Subsequently, the total figure will be converted to percentage [the best (203) and worst (29) scores will be equivalent to 100% and 0%, respectively].

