13.1.3 Efficacy analysis

From FAS the following shall be analyzed.

<Primary endpoint>

Change from baseline (Week 0) in total score for all question items in the DTR-QOL Questionnaire at the end of the treatment period (Week 12).

- 1) A comparison between the treatment groups will be carried out based on the ANCOVA model using "the change in the total score by the end of treatment [the end of the treatment period - baseline (Week 0)]" as a dependent variable; "the total score at the baseline, the total score of the DTR-QOL Questionnaire (<80% or ≥80%) at the start of the screening period and HbA1c (<8.0% or ≥8.0%) at the start of the screening period as covariates; and "a treatment group" as an independent variable. The level of significance will be 5% (two-sided).

<Secondary endpoints>

Efficacy endpoints:

- Changes in the total score for each factor provided through the DTR-QOL Questionnaire [“Factor 1: Burden on social activities and daily activities (13 questions in all)”, Factor 2: Anxiety and dissatisfaction with treatment (8 questions in all), “Factor 3; Hypoglycemia (4 questions in all)”, and “Factor 4: Treatment satisfaction (4 questions in all)”] at each assessment time point.
- Change in the total score for all questions in the DTR-QOL Questionnaire at each assessment time point.
- Change in the total score for treatment satisfaction in the DTSQ (evaluated with the score of questions #1, 4, 5, 6, 7, and 8) at each assessment time point.
 - 1) Summary statistics [sample size, mean, standard deviation (SD), maximum, minimum and quantile] and the two-sided 95% confidence interval (CI) for means per treatment group at each assessment time point will be calculated to plot the changes in means and SDs. Point estimates and the two-sided 95% CI for differences between the treatment groups will also be calculated.
 - 2) Changes from the baseline (Week 0) to each assessment time point will be calculated to be similarly analyzed to 1) above.

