8.5 Preparation and storage of allocation list

The allocation responsible person (designated by the sponsor) shall create an allocation list.

Study subjects will be allocated at the Case Registration Center through the Case Registration Web System, using "the total score for the DTR-QOL Questionnaire [$<80\%$ (<168.2 as a score) or $\geq 80\%$ (≥ 168.2 as a score[※])]" and "HbA1c ($<8.0\%$ or $\geq 8.0\%$)" at the start of the screening period as stratification factors. The Case Registration Center will use the allocation list for stratification prepared by the allocation responsible person in operating the treatment allocation.

※ Refer to the section 9.1.9 for the calculation method of the total score for the DTR-QOL Questionnaire.

Information on the allocation shall be kept in a safe place and shall not be available to anyone other than authorized persons, to secure independency from the clinical research.

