End of Study	The latest date in treatment period	21～97

2) DTSQ, Laboratory Test (except HbA1c)

Analysis Visit	Reference Day	Time Allowance (Number of Study Days)
Week -4	-30	-30～-2
Week 0	-1	-1
Week 4	28	21～35
Week 12	84	70～97
End of Study	The latest date in treatment period	21～97

OTHER DATA HANDLING

Items	Method	Conditions
DTR -QOL Questionnaire Factor1: Burden on Social Activities and Daily Activities	The sum total of questions number 1 -13 was converted into a 0 -100 score [the best (91) = 100 and worst (13) = 0].	For a factor with <50% missing data, the mean value (round off 2 digits) calculated from available answers is applied to cover the missing data.
DTR -QOL Questionnaire Factor 2: Anxiety and Dissatisfaction with Treatment	The sum total of questions number 14 and 19 -25 is converted into a 0 -100 score [the best (56) = 100 and worst (8) = 0].	For a factor with <50% missing data, the mean value (round off 2 digits) calculated from available answers is applied to cover the missing data.
DTR -QOL Questionnaire Factor 3: Hypoglycemia	The sum total of questions number 15 -18, and is converted into a 0 -100 score [the best (28) = 100 and worst (4) = 0].	For a factor with <50% missing data, the mean value (round off 2 digits) calculated from available answers is applied to cover the missing data.
DTR -QOL Questionnaire Factor 4: Treatment Satisfaction	Each score of question number 26 -29 is reversed (i.e., 1 converted to 7, 7 converted to 1, and so on; the converted scores, where 7 is the best	For a factor with <50% missing data, the mean value calculated from available answers is applied to cover the missing data.

Items	Method	Conditions
	and 1 is the worst, had the opposite sequence of the original scores). The converted scores are then added up, and the total is converted into a 0 -100 score [the best (28) = 100 and worst (4) = 0].	
DTR -QOL Questionnaire Total Score of all Questions	1) Each score of question number 26 -29 was reversed.((i.e., 1 converted to 7, 7 converted to 1, and so on;). Factor1 – Factor 4 are calculated as described above.(Not converted) 2) Factor 1 - Factor 4, which calculated by the method described above, are subsequently added up, and converted into a 0 -100 score [the best (203) = 100 and worst (29) = 0].	The total score of whole questions is not calculated if a total score of any of the four factors was unavailable.
DTSQ Total Score	Item 1, 4, 5, 6, 7, 8 scores are added up,	All data must not be missing.

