1.2 Demographics and Other Baseline Characteristics**1.2.1 Distribution of Demographics Items**

Analysis Set: Full Analysis Set

Items: Age (years) [Min<= - <65, 65<= - <75, 75<= - <=Max]

Gender [Male, Female]

Height (cm) [Min<= - <150, 150<= - <160, 160<= - <170, 170<= - <=Max]

Weight (kg) [Min<= - <50.0, 50.0<= - <60.0, 60.0<= - <70.0, 70.0<= - <80.0, 80.0<= - <=Max]

BMI (kg/m2) [Min<= - <18.5, 18.5<= - <25.0,

	25.0<= - <=Max]
Smoking Classification	[Never smoked, Current smoker, Ex-smoker]
Drink Alcohol Almost Every Day?	[Yes, No]
Duration of type 2 Diabetes Mellitus (years)	[Min<= - < 5, 5<= - <10, 10<= - <=Max]
Any Medication for Concurrent Condition?(Week 0)	[Yes, No]
Number of Daily Doses of Drugs (Concurrent Condition Medicine.)	[Less than 2 Times, 2 Times or More]
Total Number of Daily Tablets (Concurrent Condition Medicine.)	[Less than 2 Tablets, 2 Tablets or More]
Number of Doses of Drugs (Study drug.)	[Once a Week, Once daily, Twice daily]
HbA1c (Week -4)	[Less than 8.0%, 8.0% or more]
DTR -QOL Total Score (Week -4)	[Less than 80, 80 or more]
DTR -QOL Total Score (Week 0)	
DTR -QOL Total Score of "Factor 1: Burden on Social Activities and Daily Activities" (Week 0)	
DTR -QOL Total Score of "Factor 2: Anxiety and Dissatisfaction with Treatment" (Week 0)	
DTR -QOL Total Score of "Factor 3: Hypoglycemia" (Week 0)	
DTR -QOL Total Score of "Factor 4: Satisfaction with Treatment" (Week 0)	
DTSQ Total Score (Week 0)	
Method:	For the above analysis items, the following analysis will be performed for each treatment group and total.
	(1) Summary of frequency distribution for discrete variables and summary statistics for continuous variables.

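### The protocol summary misprints the 80% stratification cut-off as 139.4 (it is 168.2), and the SAP's ANCOVAs drop the Week 0 score that the protocol lists as a covariate

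*Protocol*

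**What the plan says.** **Cut-off.** The study summary (Protocol 2.0) reads "Randomization was stratified by the total score (<80% (score 139.4), ≥80% (score 139.4". Its footnote describes the score as "expressed as a percentage of the maximum total score", then anchors 203 at 100% and 29 at 0%. Protocol 8.5, which governs the allocation list, puts the lower stratum at "<168.2 as a score" and refers to 9.1.9 for the calculation. Section 9.1.9 says of the total score: "the best (203) and worst (29) scores will be equivalent to 100% and 0%, respectively". Both protocol versions in the file carry both figures. The SAP works on the converted scale only: its data-handling table has the total "converted into a 0 -100 score [the best (203) = 100 and worst (29) = 0", and SAP 1.2.1 tabulates the screening score as "Less than 80, 80 or more".

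**Covariates.** For the primary ANCOVA, Protocol 13.1.3 item 1 begins its covariate list with "the total score at the baseline, the total score of the DTR-QOL Questionnaire" and continues with the two screening categories (DTR-QOL at 80%, HbA1c at 8.0%). The summary says the same and names the visit: "the total score at the baseline (Week 0), the total score of the DTR-QOL Questionnaire". Item 3 of the secondary analyses also lists the Week 0 score, together with Week 0 categories. SAP 2.1 names only the two screening categories, and SAP 2.2(2) only the two Week 0 categories. SAP 2.4.1 adds nothing and points back to 2.1 and 2.2.

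**The concern.** A randomisation threshold should have one printed value. Whole raw scores from 140 to 168 fall in different strata under the two figures, so a system or site working from the summary would have stratified differently from Protocol 8.5.

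The covariate mismatch concerns the single primary test. Protocol 13.1 leaves detailed methods to the SAP, but the SAP gives no reason for removing a covariate that the protocol names, and neither document says which list prevails. The two models can give different estimates and p-values from the same data. In an open-label trial with a self-reported endpoint, the choice should not be left open. Subtracting the Week 0 score does not replace adjusting for it: a change score fixes the slope on baseline at 1, whereas ANCOVA estimates it. The screening category controls a chance Week 0 imbalance only coarsely.

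**Working it through.** **1. Cut-off**

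Inputs: minimum 29 and maximum 203 (Protocol 2.0 footnote and 9.1.9), so the range is 174.

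- Protocol 8.5 reproduced: 29 + 0.80 × 174 = **168.2**.
- The summary's figure converted back: (139.4 − 29) / 174 = **63.4%**.
- Gap: 168.2 − 139.4 = 28.8 raw points, or 80 − 63.4 = 16.6 percentage points.
- The footnote taken literally as a share of the maximum: 0.80 × 203 = 162.4, not 139.4.
- Minimum not added back: 0.80 × 174 = 139.2. This is 0.2 from the printed figure, which suggests a slip but does not prove one.

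**2. Which covariates each document lists**

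| Model | Protocol 13.1.3 | SAP |
|---|---|---|
| Primary | Week 0 total score; screening DTR-QOL category; screening HbA1c category | 2.1: the two screening categories |
| Secondary | Week 0 score; Week 0 DTR-QOL category; Week 0 HbA1c category | 2.2(2): the two Week 0 categories |

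The protocol does not use the word continuous. Because it lists the score in addition to the 80% category, the score is read here as a separate, continuous covariate.

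**3. The plan's sample size, as a check**

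Inputs (Protocol 13.3): mean changes 14.4 and 19.0, difference 4.6; SD 12.1; two-sided 5%; 110 per group. An unadjusted two-sample t-test has power 80.1%, which reproduces the stated 80%. Allowing for 8% loss, 110 / 0.92 = 119.6, giving 120. The sample size does not depend on the covariate.

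**4. Precision lost in the primary model**

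The documents give no correlations, so these are assumptions:

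- ρ = corr(Week 0, Week 12), 0.4–0.8.
- r = corr(screening, Week 0), 0.7–0.9.
- q = corr(screening, Week 12), either rρ or the smaller of ρ and r.
- The 80% cut lies z = 0 to 2 SD above the screening mean.
- Normal scores, equal variances, HbA1c ignored.

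Let k² = φ(z)² / [p(1 − p)], with p the share above the cut. With unit variances, the residual variance of the change is:

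- category only (SAP): A = 2(1 − ρ) − k²(q − r)²
- category plus Week 0 score (protocol): B = 1 − ρ² − k²(q − rρ)² / (1 − k²r²)

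The two ends of the range for A/B:

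- *Smallest loss* (ρ = 0.8, r = 0.9, z = 0, q = rρ = 0.72, k² = 0.637): A = 0.4 − 0.637 × 0.18² = 0.379; B = 1 − 0.64 = 0.36. A/B = 1.054; SD ratio 1.027.
- *Largest loss* (ρ = 0.4, r = 0.7, z = 2, q = 0.4, k² = 0.131): A = 1.2 − 0.131 × 0.3² = 1.188; B = 0.84 − 0.131 × 0.12² / (1 − 0.131 × 0.49) = 0.838. A/B = 1.418; SD ratio 1.191.

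Omitting the Week 0 score therefore raises the residual SD by 2.7–19%. That equals needing 5–42% more subjects for the same precision.

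**5. Power** (difference 4.6, raw change SD scaled to 12.1, 110 per group, noncentral t)

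| | SAP covariates | Protocol covariates |
|---|---|---|
| Smallest-loss case | 82.2% | 84.1% |
| Largest-loss case | 80.5% | 91.9% |
| Whole range | 80–86% | 84–92% |

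The gap within a scenario is 2–11 points. A separate simulation used r = 0.8, ρ = 0.3–0.7, 20% or 50% in the upper stratum and a normal approximation. It gave 81–85% against 87–94%.

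**6. Secondary models**

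With an assumed factor-to-total correlation of 0.6–0.9 and ρ = 0.4–0.8, omitting each outcome's own Week 0 value raises the residual SD by 2.7–19%.

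**The case against.** On the cut-off, the documents largely answer themselves. The criterion is 80% throughout, 8.5 is the operative section and is right, the summary's own anchors let a reader correct the figure, and the SAP uses the 0–100 score, so 139.4 enters no analysis. Nothing shows that it was ever configured. All of this stands, and on its own the point is minor.

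On the covariate, both models are valid under randomisation, the sample size came from an unadjusted comparison, and 80% power is met either way. The size of the loss rests on correlations that the documents do not give; only its direction is firm. That also stands, so the case should rest on having one prespecified primary model, with the power figures as illustration.

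It can also be argued that Protocol 13.1, by sending detailed methods to the SAP, gives the SAP the last word. That carries less weight: detailing a method is different from removing a named covariate without comment. The SAP's revision history describes version 2.0 as following the revised protocol, yet the mismatch remains. Lost text is an unlikely explanation, because both SAP sentences are complete and the same term is missing from each.

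**Conclusion.** Both parts hold. The summary's 139.4 is wrong on the protocol's own scale, by 28.8 raw points; the correct value is 168.2. If the registration system held 168.2, allocation and analysis are unaffected.

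The covariate discrepancy is the reason to act. The protocol and SAP specify different primary ANCOVAs, and the secondary ANCOVAs differ in the same way. There is no bias and no loss of type I error control. The cost of the SAP version is an open choice of primary model and some precision, put at 2–11 points of power under the assumed correlations and with 12.1 taken as the unadjusted SD of change.

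**What to change.** 1. In the protocol summary, replace 139.4 with 168.2 and reword the footnote to the 29–203 rescaling of 9.1.9. Confirm the value held in the Case Registration Web System. If it was 139.4, define the stratum covariate by the stratum actually used at randomisation.
2. In SAP 2.1, add the continuous Week 0 DTR-QOL total score. In SAP 2.2(2), add the continuous Week 0 value of the outcome being analysed. Both then match Protocol 13.1.3 items 1 and 3.
3. While editing, name the covariates behind the adjusted mean differences in SAP 2.2(1), which lists none.
4. Optional, for consistency only: use the as-randomised screening strata in the secondary ANCOVAs. The Week 0 categories now specified cause no bias.

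The cost is one configuration check, one corrected figure and footnote, and short edits to SAP 2.1 and 2.2. No data are added and no subjects are lost, because a change score already requires the Week 0 value.
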